The user interface of the device was designed with feedback from Malawian doctors and nurses. The baby's temperature is displayed continuously on the battery powered control box; if the infant's temperature drops below 36.5°C , a blue light atop the box flashes to signal that intervention is necessary. Similarly, if the infant's temperature exceeds 37.5°C , a red light flashes signaling for intervention. The light flashes speed up with degree of hypo- or hyperthermia.

NTM has important advantages compared to two other approaches which have been developed to address this need (Table 1). Unlike Bempu, a wrist-worn monitor that provides an audible alarm, NTM is placed over the liver to measure core temperature and it displays temperature continuously. Neonatal nurses on our development team identified

Table 1: Options for low cost neonatal temperature monitoring

	NTM	Bempu	ThermoSpot
Benefits	Easy to understand continuous visual cues and digital temperature display, no disposables	Audiovisual alarm, intuitive, also suitable for in home use	Visual cue for different levels of hypothermia, low cost, no power required
Cost	\$10	\$30 (2000 Rs) Bempu.com	\$0.50 Maternova.net

temperatures above 36.5°C, brown between 35.5 and 36.4°C, and black below 35.5°C) it is not reusable and the color change can go unnoticed without scheduled monitoring.

In this study we plan to evaluate the ability of NTM, Bempu, and ThermoSpot to detect hypo- and hyperthermia in neonates by comparing to a gold standard electronic temperature monitor used in high-resource settings.

F. Rationale/Justification for the research project

Together, prematurity and infection account for more than 50% of neonatal mortality globally, resulting in a combined 1.7 million deaths each year [5]. Improved ability to monitor neonatal temperature could help improve outcomes for both preterm babies, who are at high risk of hypothermia, as well as babies with infections, who are at high risk of hyperthermia. In many low-resource settings, routine monitoring is simply not possible due to staff and equipment shortages. Our innovation, NTM, offers an affordable, rugged, low-power tool that provides constant monitoring with digital display of temperature and a simple light to notify a guardian or nurse when intervention is necessary. Furthermore, NTM is reusable, requires no consumables, and has a very simple design to facilitate easy maintenance and repairs.

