1. Prior to the start of the study, all study nurses/clinicians will receive training on how to use the test devices. Clinical decisions will still be based on the standard of care, which will not be interrupted during the study. The study nurse/clinician will apply the temperature sensors to the infant.
2. A research technician will be available for the duration of the study to record the data from the monitors.

Enrollment :

Enrollment will take place after fully informed and written consent from the parent or guardian. A parent will be free to withdraw their child from participating at any time, without explanation and without detriment to ongoing care. There will be no financial benefit to participants though the infants will benefit from close monitoring. A participant identification number will be assigned. This number will be used for identification purposes throughout the study.

Monitoring of Neonates:

During the trial, the following steps will be taken:

A trained study nurse will assess the subject for clinical complications before attaching the temperature monitoring device.

- 1) A trained study nurse or clinician will attach the three test temperature monitoring devices to the infant. A trained research assistant from Rice University or from the Biomedical Engineering Department at Malawi Polytechnic will observe all procedures and will notify the nurse of any observed errors so they may be corrected. They will also be able to answer any technical questions from the nurse.
- 2) The trained study nurse will attach the temperature probe from the commercial gold standard as well as provide any other care needed.
- 3) A research assistant will use a laptop to collect data from the continuous temperature monitors (NTM and gold standard). The nurse will record the temperature readings every hour from all monitors on paper forms along with the standard of care.
- 4) Each time an alarm sounds from any device (Bempu and the commercial gold standard have audible alarms), the nurse will record all temperature values including a reading taken with the standard of care method. If the subject is found to be hyper/hypothermic, the nurse will respond with the appropriate standard of care.
- 5) Temperature monitoring will continue for up to 3 days. The research assistant may ask the nurse to remove and reapply the temperature probes during this period.

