A research assistant will be available during the trial to mitigate any complications with the devices. If the subject's guardian, the nurse, or the research assistant indicates concern during the tests, temperature monitoring will be discontinued and the subject's treatment will return to the standard of care. The nurse can choose to remove one of the test devices and continue the study with the remaining monitors if any issue arises.

Clinical data will be collected on paper forms as is consistent with current clinical practice. Data from the temperature monitors will be saved on a secure study server for analysis. Clinical and/or research personnel will record information, excluding personal identifiers, on a standardized patient monitoring form. After the subject's participation is complete, a research assistant will collect and scan the form.

The following section details the variables that will be measured or calculated in the study.

Intended Data Collection:

1. Baseline demographic and relevant medical information
 - a. Recorded once at enrollment
 - i. Date of Study
 - ii. Date of Birth
 - iii. Sex
 - iv. Birth Weight
 - v. Type of delivery
 - vi. Gestational age at birth
 - vii. Corrected gestational age
 - viii. Abdominal circumference
 - ix. Admission Temperature
 - b. Recorded throughout study as clinically collected
 - i. Other comorbidities
 - ii. Medications/treatments given
 - iii. Current weight
 - iv. Additional temperature measurements taken as standard of care
2. Accuracy
 - a. Recorded automatically by study equipment
 - i. Abdominal temperature and alarms from Rice designed temperature monitor and gold standard device
 - b. Recorded every hour by study nurse or as alarm events occur
 - i. Temperature measurements from other devices
 - ii. Temperature measurements using standard of care method (axillary)
 - iii. Ambient temperature
 - iv. Current thermal treatment, if any
 - c. Movement/other caregiving
 - d. Fit/tightness of the devices

A log of observed user error and comments may be used to improve the usability of the test devices.

[vii] Data Management and Analysis

Personal identifiers will be removed from the data which will be kept on a secure server accessible only to study personnel.

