The accuracy of the temperature sensors will be determined by calculating the difference between the temperatures recorded by the temperature sensor and the commercial patient monitor at each point in time. The average error between the temperature sensor and the gold standard will be calculated for each subject and compiled in a Bland-Altman plot. The 95% limits of agreement will be calculated. Our target error is less than +/- 0.5 C.

For the devices that do not provide a continuous numerical reading, the recorded state every hour will be compared to the gold standard at that point in time. The sensitivity and specificity for hypo/hyperthermia will be calculated for each device.

The ability of each device to accurately diagnose hypothermia will also be calculated with respect to the alarm events for each device for which they were recorded. The sensitivity and specificity will be determined using the number of false alarms collected during the study.

As a secondary analysis, the errors will be plotted against thermal treatment type and ambient temperature to determine their confounding effects on accuracy. An ANOVA will be used to determine statistical significance.

The research team from Rice University and QECH will be responsible for all data analysis. We plan to analyze data using Excel, MATLAB, and associated statistics packages.

[viii] Results Presentation

Statistical analysis will be performed and means, limits of agreement, sensitivities and specificities will be reported. Tables and graphs may also be used to present any additional correlations, explain outliers, or demonstrate confounding effects.

[ix] Dissemination of Results

The results of this study will be made available to the Ministry of Health, COMREC, the College of Medicine Library, the Department of Paediatrics, and other partners working in neonatal and child health. A copy of the final report and any published papers or abstracts will be submitted to The Health Sciences Research Committee and the University Research and Publication Committee (URPC) through the COMREC Secretariat. Findings will be published in academic journals and conference

proceedings in an effort to disseminate results to potential end-users. The research findings of this study will be critical in the evaluation of future interventions.

I. Ethical considerations

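### The nurse judges the ThermoSpot colour on the same occasions as the numeric readings, with no reading order or masking stated, so its sensitivity and specificity are open to review bias

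*Combined protocol and SAP*

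**What the plan says.** **Recording.** Section H [vi], Monitoring of Neonates, step 3: "The nurse will record the temperature readings every hour from all monitors on paper forms along with the standard of care". Step 4 covers each audible alarm: "the nurse will record all temperature values including a reading taken with the standard of care method". The same step notes that Bempu and the gold standard have audible alarms.

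**Automatic capture.** Step 3 also says: "A research assistant will use a laptop to collect data from the continuous temperature monitors (NTM and gold standard"). Intended Data Collection, item 2a, lists as automatically recorded: "Abdominal temperature and alarms from Rice designed temperature monitor and gold standard device". Item 2b leaves to the nurse, hourly or at alarms, "Temperature measurements from other devices", together with the axillary temperature, the ambient temperature and the current thermal treatment.

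**What is on show.** Section E says of the NTM: "The baby's temperature is displayed continuously on the battery powered control box". It adds that a blue light flashes below 36.5 °C. ThermoSpot is described as green above 36.5 °C, then "brown between 35.5 and 36.4°C, and black below 35.5°C".

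**Analysis.** Section H [vii] says that, for devices without a continuous numerical reading, "the recorded state every hour will be compared to the gold standard at that point in time". Sensitivity and specificity follow for each device. A separate paragraph deals with alarm events.

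**The concern.** In an accuracy study, the result of the device under test should be read without knowledge of the reference result. The ThermoSpot colour is the read-out here that depends most on the observer's judgement, and the hard calls are between green and brown. That boundary is the temperature at which the protocol defines hypothermia, so any number the nurse has just seen tells her which colour to expect. At an alarm, the gold standard may already have announced its own result.

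The stated aim is to find which low-cost tool is most accurate and effective. The exposure is unequal across devices. The NTM's continuous comparison can rest on laptop data, whereas ThermoSpot rests on the nurse's entry alone. Any resulting bias would distort the comparison between devices, and it would not shrink with more data.

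**Working it through.** **1. Is the exposure in the text?** Four statements, set side by side:

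| Question | Where | Answer |
|---|---|---|
| Who records the ThermoSpot colour? | H [vi], steps 3 and 4 | The nurse, who also records all the other monitors and the standard-of-care reading |
| Is there any other record of the colour? | H [vi], step 3; Intended Data Collection 2a and 2b | None listed; only the NTM and the gold standard are logged automatically |
| Is the colour kept independent of the numbers? | Sections E and H | No order, covered display, separate reader or photograph is stated |
| Is that entry what gets scored? | H [vii] | Yes, the hourly recorded state against the gold standard |

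That the displays are visible when the colour is judged is an inference. It follows from one nurse recording every monitor on one occasion, a continuously lit NTM display, and no masking step. Item 2b can be read as having the nurse write down fewer numbers than step 3 does. Even so, she still takes the axillary reading and the NTM display is still there.

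**2. How large could it be?** The plan gives no expected sensitivity or specificity and no rate of altered readings, so there is no figure to reproduce. The values below are assumptions.

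*Upper case: every shift is toward the gold standard.* Let s be the true sensitivity or specificity, and q the share of discordant colours recorded to match the gold standard. Then observed = s + q(1 − s). Assume sensitivity 0.70 and specificity 0.85:

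| q | Observed sensitivity | Observed specificity |
|---|---|---|
| 0.1 | 0.70 + 0.1 × 0.30 = 0.73 | 0.85 + 0.1 × 0.15 = 0.865 |
| 0.3 | 0.70 + 0.3 × 0.30 = 0.79 | 0.85 + 0.3 × 0.15 = 0.895 |
| 0.5 | 0.70 + 0.5 × 0.30 = 0.85 | 0.85 + 0.5 × 0.15 = 0.925 |

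*Shift toward the NTM display instead.* Now let q be the share of colours disagreeing with the NTM that are recorded to match it. Then observed sensitivity = (1 − q) × Se + q × Se(NTM). With Se = 0.70 and an assumed Se(NTM) of 0.80:

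- q = 0.3: 0.7 × 0.70 + 0.3 × 0.80 = 0.73
- q = 0.5: 0.5 × 0.70 + 0.5 × 0.80 = 0.75

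The gain is a third or less of that in the upper case at q = 0.3 (0.03 against 0.09) and at q = 0.5 (0.05 against 0.15). If the NTM's sensitivity were below 0.70, the observed value would fall. Both formulas also treat every discordant colour as equally open to change, although only borderline colours plausibly are.

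**3. Does the volume of data help?** The ceiling is 60 infants × 3 days × 24 readings = 4,320 hourly records per device. Neither formula contains the number of readings, so the bias is the same at any volume.

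**The case against.** Several points on the other side stand.

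- **Visibility and order.** A reader might infer that the plan has the nurse judge the colour while looking at the gold-standard number. No sentence says so. A standardised monitoring form is mentioned but not reproduced, and it may already fix an order. What can be said is that the protocol text states none.
- **Inflation.** A reader might take inflated sensitivity and specificity as certain. The documents do not support that. The nurse has three numbers available (NTM, gold standard, axillary), and a shift toward one that disagrees with the gold standard could help less, or hurt.
- **Bempu.** A reader might extend the point equally to Bempu. Table 1 describes an audiovisual alarm, which is a state the device generates. It could be missed or noted selectively, but it is not a borderline colour.
- **Existing safeguards.** The NTM and the gold standard are already to be logged automatically, and the hourly comparison already stands in a different paragraph from alarm events. Neither safeguard is absent.

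Three further objections carry less weight. Accuracy when used by nurses is an objective, but that justifies nurse reading, not reading beside the reference; the Executive summary says electronic monitors are unavailable in the target settings. This is a pilot, but its results are to be published and sent to the Ministry of Health. Leaving out readings near 36.5 °C would probe the mechanism afterwards, but it would not restore independence to the readings that matter most.

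**Conclusion.** The point holds for ThermoSpot. As the protocol is written, its colour is recorded on the same hourly and alarm occasions as the numeric values, with no stated safeguard and no second record of the colour. Its sensitivity and specificity are therefore open to review bias. The likely direction is toward better agreement, on the assumption that the numbers the nurse sees mostly agree with the gold standard.

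Confidence is high that no safeguard is stated in the protocol text. It is not high for the occurrence, direction or size of any bias. The figures up to 0.85 and 0.925 are an illustrative upper case built on assumed values. Bempu is much less exposed, and the NTM's continuous comparison is largely unaffected if it uses the laptop data. The change should be made before enrolment, because independence lost at the time of reading cannot be recovered later.

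**What to change.** 1. Order the hourly and alarm forms so that the ThermoSpot colour is written first, before any numeric value is looked at or recorded. The Bempu state comes next, then the axillary, NTM and gold-standard values. A colour entry is not revised afterwards. If the form already has this order, one protocol sentence is enough.
2. Add one line on this to the nurse training.
3. State in Section H [vii] that the reference for the hourly comparison is the time-stamped automatic log already planned, not the nurse's transcription.
4. State there too that scheduled hourly readings and alarm-triggered readings are analysed separately, as the section already implies.

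**Cost:** a reordered paper form, a training line and a sentence or two of analysis text. The sample size does not change. **Limits:** the NTM display and light stay in the room and the previous hour's values are known, so the bias is reduced, not removed. The change concerns recording only and must not delay standard care.

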A. Title

Assessment of low-cost temperature monitoring tools for neonates.

B. Investigators

Principal Investigator: [name], College of Medicine, Blantyre, Malawi

Co-Investigators: [name], Dept. of Bioengineering, Rice University, Houston, TX USA
[name], Dept. of Bioengineering, Rice University, Houston, TX, USA
[name], Rice 360: Institute for Global Health, Rice University, Houston TX, USA
[name], Rice 360: Institute for Global Health, Rice University, Houston TX, USA
[name], Rice 360: Institute for Global Health

Investigators' CVs: Please see Appendix 1

C. Institutions under whose umbrella the research project will be conducted

- [i] College of Medicine, Blantyre, Malawi
- [ii] Rice University, Houston, TX, USA

D. Executive summary

Problem statement: Neonatal hypothermia is a pervasive global challenge; as many as 85% of infants born in hospitals in low-resource settings are too cold (defined as a temperature <36.5C) [1]. A recent study of 23,240 newborns in Nepal showed that babies with moderate hypothermia are nearly five times more likely to die than normothermic infants; the risk of death is more than 23 times higher for babies with severe hypothermia [2]. While the risks of being too cold are well recognized, hypothermia remains a largely invisible problem in overcrowded newborn units in low-resource settings. Electronic temperature monitors used in high resource settings are not available in low-resource settings because they are too costly or require a constant supply of consumable thermistors. Simple digital or analog thermometers are often unavailable; when they are available, wards are often too short-staffed to permit routine monitoring at regular intervals.

Aim of Study: A team of researchers at Rice University and QECH are working to develop a low-cost temperature sensor that can continuously monitor an infant's temperature (NTM). This robust, low-cost device will allow for the individualized monitoring of each infant with alerts for hypo and hyperthermia. A reusable band to

hold the temperature sensor will eliminate disposable components. This study will assess the accuracy of this novel device against a gold standard along with existing low cost temperature monitors, ThermoSpot and Bempu, to determine which tool is most accurate and effective for neonatal wards.

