This study is the first step in a systematic evaluation of NTM in comparison to the gold standard of electronic monitors used in high resource settings as well as two other alternatives specifically designed for low-resource settings: Thermospot and Bempu. Both are easy to use and can diagnose need for thermal care at a glance. Thermospot is a low-cost, one-time use disposable system that requires no power. Bempu is a \$30 temperature monitoring bracelet that can run continuously for 30 days at which time it is replaced. A careful evaluation and comparison of these three solutions will provide critical data to support improved access to continuous temperature monitoring in low-resource settings. Future studies may evaluate not only the accuracy of these tools, but how they affect nurse/caregiver behavior and influence patient outcomes.

continuous display of temperature as one of the most highly desired features of NTM because it would help improve the care they can provide while reducing their workload. Thermospot, a temperature sensitive sticker, is another alternative to monitor neonatal temperature. While Thermospot changes color to indicate temperature (green at

G. Objectives of the study

[i] Broad

The purpose of this study is to determine if three low-cost temperature monitoring devices can: 1) accurately measure neonatal temperature in a low-resource clinical setting, and 2) serve as an easy to use tool for monitoring temperature in low-resource settings.

[ii] Specific

The specific objectives for the current stage of this project are:

1. To determine the accuracy of the NTM, Bempu, and ThermoSpot devices when used by nurses in the neonatal ward by comparing
 - a. Continuous temperature measurements
 - b. Periodic temperature measurements
 - c. Temperature during alarm events
2. To ensure the NTM is easy to understand and use in the
 - a. Nursery with open cots, hot cots, and radiant warmers
 - b. KMC ward

H. Methodology

[i] Study Type

This is a **pilot comparative study** to determine the level of agreement between three low cost temperature monitors against a continuous commercially available gold standard. The accuracy will be assessed both on infants in the neonatal ward as well as infants undergoing Kangaroo Mother Care (KMC).

[ii] Place of Study

This clinical study will take place at Queen Elizabeth Central Hospital (QECH) in Blantyre, Malawi. Patients will be recruited as they are admitted to the neonatal or KMC wards.

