The subject may be removed from the study at any time at the request of the parents or clinicians. Axillary temperature measurements given as the standard of care will continue during the study and will not be interrupted.

After each subject, the devices will be cleaned thoroughly with a bleach solution.

There is the potential risk of the loss of confidentiality associated with participation in this study. No patient identifiers will be collected by the study. All patient data will be assigned a number to ensure subject confidentiality. All efforts will be made to maintain strict patient confidentiality.

K. Study Requirements

The study will require the following:

Personnel:

[name], College of Medicine, Blantyre, Malawi: Principal Investigator
Research technician: A researcher from Rice University will travel to Blantyre (supported by Rice University).
Study nurse: [name]

Training:

Prior to the start of the study, all study nurses/clinicians will receive training on the use of the test devices by the Rice research team. Each member will pass a standard evaluation in order to operate the device. The Rice researcher and [name] will be available on site or by phone, email, and site visits to respond to any questions and/or concerns. The US- based investigators will be in frequent contact with the local team.

Paper: The Rice researcher will provide all consent and monitoring forms.

Equipment: The temperature monitoring devices will be provided by Rice for the study.

No transport, reagents, drugs or additional space will be required for the study.

L. Budget and budget justification

Salary Description	Cost
[name] Honorarium	\$1500
Study Nurse	\$600
Printing Costs	\$150
Direct Costs Total	\$2250
10% F&A Costs	\$225
Total	\$2475

The test devices and paper forms (consents and monitoring forms) will be provided by Rice University. We have received funding from private donors to support this study.

This study is part of a larger plan to investigate and implement low cost temperature monitoring tools in neonatal wards. We estimate that this study comprises 30% of that work, for which an honorarium of \$5000 was assigned. Therefore, we have listed the appropriate proportion of that honorarium here.

N. References

1. Lunze et al. *J Perinatol*. 2012 May;32(5):317-24.
2. Mullany et al *Arch Pediatr Adolesc Med*. 2010;164(7):650-656.
3. Waldron et al. *Infant Journal*. 2007 May; 3(3).

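### A research assistant not stated to be blinded to the NTM-reference difference may prompt probe reapplication at will, so NTM may look more accurate than in nurse use

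*Combined protocol and SAP*

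**What the plan says.** All references are to the combined protocol and SAP.

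- **Objective (G [ii], item 1).** "To determine the accuracy of the NTM, Bempu, and ThermoSpot devices when used by nurses in the neonatal ward by comparing" continuous readings, periodic readings and temperature during alarms.
- **Data capture (H [vi], Monitoring of Neonates, step 3).** "A research assistant will use a laptop to collect data from the continuous temperature monitors (NTM and gold standard". The nurse also writes down the readings of all monitors every hour.
- **Reapplication (same section, step 5).** "The research assistant may ask the nurse to remove and reapply the temperature probes during this period". No time, trigger or limit is given, and the devices covered are not named.
- **Who the assistant is (step 1).** "A trained research assistant from Rice University or from the Biomedical Engineering Department at Malawi Polytechnic will observe all procedures". This person "will notify the nurse of any observed errors so they may be corrected". The executive summary says of NTM: "A team of researchers at Rice University and QECH are working to develop a low-cost temperature sensor".
- **Stopping (H [vi], after step 5).** "If the subject's guardian, the nurse, or the research assistant indicates concern during the tests, temperature monitoring will be discontinued". Removing a single device and continuing with the others is the nurse's choice.
- **Records (H [vi], Intended Data Collection).** Fit or tightness and movement or caregiving are recorded, and a log of user errors may be used to improve usability. Reapplications are not listed as an item to record.
- **Analysis (H [vii]).** Differences from the commercial monitor are taken at each time point, averaged per infant and shown in a Bland-Altman plot with 95% limits of agreement. The target error is below ±0.5 °C. Bempu and ThermoSpot enter as states recorded hourly and at alarms. No rule covers data around a reapplication or a stop.

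**The concern.** The planned outcome is the mean error per infant, and it depends on how long an error lasts as well as on how large it is. Step 5 gives discretion over that duration to a person who handles both the NTM data and the reference data. If reapplication is requested because NTM is seen to depart from the gold standard, the error ends because it was noticed against the reference. A ward using NTM in routine care would have no such reference beside it.

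The result could then describe NTM with reference-guided refitting rather than NTM in nurses' hands. Both the judgement against ±0.5 °C and the comparison of the three devices could be affected. NTM is the only test device with a continuous trace captured beside the reference, so any benefit would more likely fall to NTM. Because no record of reapplications is required, the effect could not be measured or removed afterwards.

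**Working it through.** **1. Is there a figure to reproduce?** No. The only related number is the sample size, 30 + 30 = 60 infants at most, which has no stated SD, precision or power behind it. The check is therefore a reading of the text plus an illustration.

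**2. Do the passages allow the mechanism?** Step 3 gives a research assistant both data streams, step 5 gives the power to request reapplication, and no section blinds the assistant. H [vi] does not require a record of the event, and H [vii] has no rule for it. So the mechanism is possible. The text does not say that it will occur.

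**3. How large could it be?** Inputs from the plan: monitoring for up to 3 days (72 h), mean error per infant, and a target of ±0.5 °C. Everything else is assumed:

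- between-infant SD 0.15 °C and within-infant SD 0.15 °C;
- sensor displacement 0.5 or 1 time per 24 h, reading 0.5 or 1.0 °C low until corrected;
- mean time to correction 12 or 6 h by the nurse alone, against 1 or 0.5 h when the assistant prompts;
- a brief half-size error after each reapplication (nominally 0.25 h);
- 4,000 simulated infants per setting.

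For infant *i*, m_i is the mean of all errors over 72 h. The limits are mean(m) ± 1.96 × SD(m). With no displacement they would be about ±1.96 × 0.15 = ±0.29 °C.

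Each cell gives mean error (°C); lower 95% limit (°C); share of time points beyond 0.5 °C.

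| Displacement | Nurse, 12 h | Nurse, 6 h | Prompted, 1 h | Prompted, 0.5 h |
|---|---|---|---|---|
| 0.5 °C, 0.5 per 24 h | -0.09; -0.44; 11% | -0.05; -0.37; 7% | -0.01; -0.31; 3% | -0.01; -0.30; 2% |
| 0.5 °C, 1 per 24 h | -0.15; -0.50; 16% | -0.09; -0.42; 11% | -0.03; -0.32; 4% | -0.02; -0.31; 3% |
| 1.0 °C, 0.5 per 24 h | -0.17; -0.64; 19% | -0.11; -0.47; 12% | -0.03; -0.33; 4% | -0.02; -0.31; 3% |
| 1.0 °C, 1 per 24 h | -0.30; -0.80; 31% | -0.19; -0.59; 21% | -0.05; -0.35; 7% | -0.03; -0.33; 5% |

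Upper limits lie between 0.20 and 0.29 °C throughout.

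A hand check on the last row: the long-run share of time displaced is d / (24/r + d), where d is the mean time to correction and r the number of displacements per 24 h. With r = 1 this is 12/36 = 0.33 for 12 h and 1/25 = 0.04 for 1 h. At 1.0 °C the mean errors would be about -0.33 and -0.04 °C. The simulated -0.30 and -0.05 °C fit: infants start well placed, and the settling error adds a little.

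**4. Against the target.** Of the eight nurse-only settings, three have a lower limit beyond -0.5 °C (-0.59, -0.64, -0.80), all with 1.0 °C displacement. One sits on the boundary (-0.50) and four meet it. All eight prompted settings meet it. Every mean error is inside ±0.5 °C, so a target read as applying to mean error would be met under either regime.

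**5. Would cutting the data at the first prompted refit repair this?** No. Take one assumed infant whose belt reads 1.0 °C low from hour 24 and is refitted at hour 25. All 72 h give -1/72 = -0.01 °C. Data up to the refit give -1/25 = -0.04 °C. The cut is itself triggered by the error, so the result stays almost as favourable.

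**The case against.** The strongest reply is that the assistant has no monopoly on the reference. The nurse writes down NTM and gold-standard readings side by side every hour and can refit a device during care. NTM also flashes blue below 36.5 °C, so a belt reading 1.0 °C low on an infant truly at 36.5-37.4 °C would signal. This stands, and it limits both the size of the problem and what any rule for the assistant can achieve. The study is also a declared pilot with openly described technical support.

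A reader might infer more than the documents support:

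- **That the assistant is the developer's own staff.** Step 1 equally allows someone from Malawi Polytechnic, which is not named as a developer. Section K says of the research technician "A researcher from Rice University will travel to Blantyre", but does not say that this person is the assistant of step 5.
- **That the assistant may end monitoring for any reason.** The wording is that concern is indicated, and guardian and nurse have the same power. Broad discretion of that kind is given only to the clinician, for exclusion (H [v]).
- **That only NTM is corrected.** Step 5 speaks of probes, a term used elsewhere for the gold-standard sensor, so the reference may be what is reapplied. Under step 1 the assistant also reports observed errors on all three test devices.
- **That reapplication will follow a mismatch.** The text says the laptop is used to collect data, not that the assistant watches the difference. Reapplication may be meant to sample placement variability, though fixed times would serve that aim at least as well.
- **That a clear failure becomes a near-perfect result.** An infant reading 1.0 °C low from hour 24 to hour 72 would have a mean error of -48/72 = -0.67 °C, against -0.01 °C if refitted after one hour. The first figure requires the nurse to pass over about 48 successive hourly mismatches, so it is an extreme case.

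None of this supplies a trigger, blinding or a record, and that gap remains.

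**Conclusion.** The concern holds as a risk of bias, not as a demonstrated bias. The plan leaves reapplication to the discretion of someone who has the reference data to hand, and requires no trace of its use. This conflicts with an objective about accuracy in nurse use. The direction probably favours NTM, but that is inferred from which devices have continuous traces. The problem arises from access to the reference combined with discretion, whoever employs the assistant.

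The size is unknown. Under the assumptions above, prompting moves the lower limit of agreement from between -0.37 and -0.80 °C to between -0.30 and -0.35 °C, and mean error from between -0.05 and -0.30 °C to between -0.01 and -0.05 °C. The result against ±0.5 °C clearly changes only with frequent or slowly corrected errors of 1.0 °C. With the smallest assumed errors it does not change. It is worth correcting before enrolment, because prompts that were not logged cannot be reconstructed later.

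**What to change.** **Step 5, H [vi].** Let the research assistant request reapplication only (a) at times set in advance, whatever the readings show, or (b) for detachment or a probe fault that can be identified without comparing NTM with the reference. Nurse-initiated care and everyone's right to stop stay unchanged.

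**Monitoring form.** For every reapplication, removal or stop, record the time, device, requester, reason and displayed values. Naming the device shows whether a test sensor or the reference probe was refitted.

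**H [vii].** Keep all on-body readings before each such event in the main analysis. Report the number of prompted reapplications per device. Give the result on data before the first unscheduled prompted reapplication as a sensitivity analysis only, since cutting there depends on the error.

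**Cost.** A sentence or two in each section and a few form columns. The NTM result may look less favourable. The change does not remove refitting by nurses who see both readings, but the log would show how often it happens.
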